## 8.2 Statistical Methods

The primary endpoints will be hemoglobin A1c at 6 months and 12 months post-enrollment. This will be analyzed and reported in two ways:

- Mean hemoglobin A1c in the study group compared to mean value at baseline
- Percentage of patients meeting treatment goal for hemoglobin A1c compared to this percentage at baseline. Treatment goal will be A1c ≤7 for most patients, A1c ≤8 for patients age 65 or older or who have 2 or more comorbidities, or other individualized goal for select patients as determined by the medical director ([name])

Secondary endpoints and analyses will include:

- Mean A1c and proportion of patients at goal at 3 months and 9 months.
- Mean FBG at 6 and 12 months compared to baseline value
- Mean BMI at 6 and 12 months compared to baseline
- Mean waist circumference at 6 and 12 months compared to baseline ٠
- Mean blood pressure at 6 and 12 months compared to baseline
- Number and percentage of patients identified as potentially having the following complications: Ischemic chest pain
  - 0
  - 0 Foot ulcers
  - Ophthalmologic complications 0
  - Hypertension 0
- Percentage of patients successfully completing referrals for potential complications
- Number and percentage of patients referred for poor glycemic control or intolerance of diabetic medications and percentage of these patients who complete referral
- Prevalence of adverse effects of metformin and hypoglycemia symptoms throughout the study
- Patient medication adherence throughout the study and at 6 and 12 months compared to baseline (proportion patient reporting each level of adherence)
- CHW compliance with medication recommendations provided by the application (proportion of visits)

Differences in continuous variables (e.g. mean A1c) will be analyzed using paired, 2-tailed t tests. Differences in categorical values (e.g. percentage of patients meeting treatment goal for A1c) will be analyzed using the McNemar test for binary matched-pairs data.

## 8.3 Subject Population(s) for Analysis

There will be no randomization and there is only one group, so all patients enrolled will be analyzed to the extent of their participation. Analyses will be as described above in section 8.2. Planned subgroup analyses include patients with A1c less than or equal to treatment goal at baseline, patients above treatment goal at baseline, and patients with A1c ≥9 at baseline.

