### Physician Oversight

Within 1-2 days of the enrollment visit and every subsequent visit, patient data from the smartphone application will be uploaded to a secure online database viewable to the supervising physician, [name]. Within 1 week of each visit, [name] will review the visit summary for each patient and either approve the current treatment or recommend changes to the treatment, including changes to the patient's glycemic target as necessary. Also during that 1 week timeframe, any changes recommended by [name] will be communicated to the patient through the health promoter coordinators and/or the health promoter who saw the patient.

If CHWs have questions regarding patient care while conducting a patient visit, they will contact one of the CHW coordinators and or [name] via telephone for advice on how to proceed.

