# 8 Study Analysis

### 8.1 Sample Size Determination

For this study, we plan to recruit approximately 150 patients based on the known population of diabetics in the rural communities surrounding San Lucas Tolimán. Of these, we hope to enroll at least 100 patients in the study. Using these numbers, statistical power was calculated using the UCSF online sample size calculators  for a one-group before-after study. The following parameters were used for calculation:

- a = 0.050
- β = 0.200
- SD for outcome = 2.4 (this was the reported pretreatment SD for A1c for a population of 174 indigenous diabetics upon enrollment in a diabetes treatment program in rural Guatemala)
- Within-subject A1c correlation coefficient (rwithin) of 0.928 (this is based on an analysis conducted to determine the accuracy and precision of the A1CNow®+ testing device49, which we are using in our study) Sample size = 100

With this sample size, we will have adequate power to detect an effect size as small as 0.257% A1c and should easily be able to detect more clinically significant differences of 1% A1c or more.

Version #: 1.0

[name]

Another primary outcome will be the proportion of patients meeting treatment goals vs this proportion at baseline. Using the above website, the same parameters for a and  $\beta$ , sample size of 100, and a baseline proportion of patients meeting treatment goals of 13% (this is based on a needs assessment that we conducted as part of this project), we would have 80% power to detect a proportion of 30.2% of patients with good glycemic control (OR 2.896 compared to baseline).

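### The Section 8.3 subgroups are cut on the same baseline A1c that the tests compare against, so McNemar can point only one way and the paired t-tests include regression to the mean.

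*Combined protocol and SAP*

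**What the plan says.** Section 8.3 of the combined protocol and SAP says "Analyses will be as described above in section 8.2". Section 8.2 offers two tests, both against each patient's own baseline. For means: "Differences in continuous variables (e.g. mean A1c) will be analyzed using paired, 2-tailed t tests". For percentages, including the percentage at the A1c goal, differences "will be analyzed using the McNemar test for binary matched-pairs data".

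Section 8.3 then lists the subgroups: "Planned subgroup analyses include patients with A1c less than or equal to treatment goal at baseline, patients above treatment goal at baseline". A third subgroup takes those whose first A1c reading is 9 or higher. It names no separate method for them, so the natural reading is that the Section 8.2 tests are run within each. There is one group and no control. The plan does not mention regression to the mean or a second baseline reading for assigning subgroups.

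**The concern.** Each subgroup is selected on the baseline A1c, and the same value then serves as the before measurement. This has two consequences.

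- **Percentage at goal.** In the above-goal stratum it is 0% at baseline and can only rise. In the at-goal stratum it is 100% and can only fall. The stratum at 9 or more also starts at 0%, unless a patient has an individualized goal of 9 or higher. One of McNemar's two discordant cells is empty by construction, so the direction of any result is settled before follow-up data exist.
- **Mean A1c.** Patients chosen for a high reading tend to read lower next time, and patients chosen for a low reading tend to read higher. The expected paired difference is therefore not zero when the program does nothing, and there is no control group to show how much of a change is this artefact.

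A significant improvement in the two high strata, or a significant loss of control in the at-goal stratum, would not by itself be evidence of benefit or harm. Section 7.4.4 says the study will inform quality improvement of a continuing program, so either misreading could influence decisions.

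**Working it through.** **Inputs from Section 8.1.** SD 2.4; within-subject correlation r = 0.928; N = 100; two-sided alpha 0.05; 13% at goal at baseline.

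**The plan's own figure.** SD of the change = 2.4 × √(2 × (1 − 0.928)) = 0.911. Detectable change at 80% power = (1.960 + 0.842) × 0.911 / √100 = 0.255 with normal quantiles, or 0.258 with t quantiles. The stated 0.257 reproduces.

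**McNemar with one empty cell.** If k patients cross and all go the same way, the exact two-sided p is 2 × 0.5^k. Five crossings give 0.0625 and six give 0.031. Section 8.2 does not name a version of the test. The continuity-corrected chi-square also needs six (p = 0.041), and the uncorrected one needs four (p = 0.046). This holds even when equal numbers cross the other way and the cohort percentage is unchanged.

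**Size of the artefact.** Assumptions: A1c normal, one goal of 7 for all, 100 completers, and no change in the cohort's mean, SD or percentage at goal. The mean that puts 13% at or below 7 is 7 + 2.4 × 1.126 = 9.70. The expected change in a stratum has size (1 − r) × 2.4 × φ(a) / P(stratum), where a = (cut − 9.70)/2.4. It is negative in the high strata and positive in the at-goal stratum. At r = 0.928:

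- ≥9: 0.072 × 2.4 × 0.382 / 0.615 = 0.11, so −0.11
- above goal: 0.072 × 2.4 × 0.212 / 0.87 = 0.04, so −0.04
- at goal: 0.072 × 2.4 × 0.212 / 0.13 = 0.28, so +0.28

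Section 8.1 says of the 0.928 that "this is based on an analysis conducted to determine the accuracy and precision of the" testing device. The correlation between readings six months apart may be lower. The documents give no such value, so 0.7 and 0.5 below are assumptions. A lower r means that patients' A1c moves over six months with zero mean change.

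Rejection rates come from 20,000 simulated trials of 100 patients per setting, with no cohort change:

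| Stratum (expected n) | r = 0.928: change; t; exact McNemar | r = 0.7 | r = 0.5 |
|---|---|---|---|
| ≥9 (62) | −0.11; 15%; <0.1% | −0.45; 49%; 1% | −0.75; 73%; 16% |
| Above goal (87) | −0.04; 7%; 10% | −0.18; 14%; 64% | −0.29; 22%; 84% |
| At goal (13) | +0.28; 18%; 10% | +1.17; 59%; 64% | +1.95; 82%; 84% |

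In the whole cohort the t-test rejects in about 5% of the same trials and exact McNemar in 1.3% to 2.8%, so the excess comes from the subgroup cut. The mean number crossing in each direction is 3.2, 6.5 and 8.3 at the three correlations. These cancel in the cohort but are split apart by the strata.

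**Sensitivity to the goal.** If 30% of patients have a goal of 8 (assumed; implied mean 10.05), r = 0.928 gives −0.09 (13%), −0.04 (7%) and +0.28 (18%), with McNemar at 10% above goal and at goal. At r = 0.7 the figures are −0.39 (42%), −0.17 (14%) and +1.15 (57%), with McNemar at 62%.

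**The case against.** Section 8.3 does not itself say that McNemar or t-tests are run inside the subgroups. Its cross-reference to Section 8.2 follows a sentence about all enrolled patients, and an analyst could simply report percentages. That is fair as a reading, but no other method is offered, and nothing steers an analyst away from the tests.

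The effect at the plan's own correlation is small in the high strata. Section 8.1 treats 1 point as a clinically significant difference, and a 1-point fall at ≥9 would be about nine times the 0.11 artefact and larger than the 0.75 at r = 0.5. This stands: a large fall would still be informative, though biased. The t-test at 7% above goal is close to nominal.

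The model is also favorable to the concern in places. One hundred completers is optimistic, since Section 8.1 only hopes to enroll at least 100 and Section 9.2.2.1 analyzes completers. With an assumed 75, exact McNemar in the above-goal and at-goal strata falls to 3–4% at r = 0.928 and about 36% at r = 0.7. The normal model puts 4.8% of patients below 5.7, which is 37% of the at-goal stratum. Dropping readings below 5.7 or above 14 lowers the at-goal t-test rejection to about 10% at r = 0.928 and about 30% at r = 0.7. These points change the size, not the mechanism. The empty McNemar cell needs no model.

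Finally, these are subgroups in a pilot study, and no sample-size claim or decision rule uses them. That limits the importance of the point, but the correction costs very little.

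**Conclusion.** The concern holds. The fixed direction of McNemar in the above-goal and at-goal strata follows from the subgroup definitions alone. It also applies at ≥9 unless an individualized goal reaches 9.

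Regression to the mean in the A1c t-tests is certain in direction but depends on the six-month correlation for its size. It is modest at 0.928 and substantial at an assumed 0.7 or below, and it is largest in the at-goal stratum of about 13 patients. The figures rest on normality, the 13% and SD 2.4 taken from Section 8.1, and 100 completers.

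The argument concerns A1c and the percentage at goal; it applies less to BMI, waist circumference or blood pressure. The whole-cohort primary analyses are not affected.

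**What to change.** In Section 8.3, state that no test against baseline is done within strata defined on baseline A1c. In place of those tests:

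- Report the percentage at goal at follow-up in the above-goal and ≥9 strata, and the percentage still at goal in the at-goal stratum, each with a 95% confidence interval.
- Score these against the goal set at baseline. The Physician Oversight text in Section 7.4.1 allows changes after any visit to the patient's "glycemic target as necessary".
- Report stratum mean A1c changes as descriptive, with a sentence that they include regression to the mean. If its expected size is shown, give it over a stated range of assumed correlations, not as a single correction.
- Base conclusions on the whole cohort.

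The cost is a few sentences and trivial programming. The subgroup results lose their p-values and look less striking. The at-goal stratum will be imprecise: 10 of 13 still at goal, for example, has a 95% Wilson interval of 50% to 92%.

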### 8.4 Planned Interim Analysis:

Initial analysis of primary endpoints and safety endpoints will occur at 3 months post enrollment to determine if any significant changes are needed to treatment protocols.

Version #: 1.0

[name]

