## 5.7 Early Withdrawal of Subjects

#### 5.7.1 Premature termination of study

This study may be temporarily suspended or prematurely terminated if there is sufficient reasonable cause. Written notification, documenting the reason for study suspension or termination, will be provided by the PI or co-investigator to the IRB. If the study is prematurely terminated or suspended, the PI will promptly inform the IRB and will provide the reason(s) for the termination or suspension.

Circumstances that may warrant termination or suspension include, but are not limited to:

- Determination of unexpected, significant, or unacceptable risk to participants
- Demonstration of efficacy that would warrant stopping
- Insufficient compliance to protocol requirements
- Data that are not sufficiently complete and/or evaluable
- Determination of futility

Study may resume once concerns about safety, protocol compliance, data quality are addressed and satisfy the IRB.

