### 7.4.4 Final Study Visit

All patients will be followed until at least 6 months post enrollment. Safety monitoring will occur on a continuous basis during the study and an interim analysis of efficacy will occur at the 6 month point. If permitted based on funding and personnel availability and the ability and desire of our local partners in Guatemala, patients will be continued to be followed out to 12 months post enrollment.

This study is based around the implementation of a program that the San Lucas Mission intends to continue indefinitely. Thus, patients who participated in this study will have the opportunity to continue their treatment through the CHW-led diabetes program. The study will inform a quality improvement process for this program and work to ensure program sustainability.

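### Sections 8.4, 4.1 and 7.4.4 disagree on when the primary endpoints are first analysed and which analysis is primary, and no error-rate or stopping rule covers the looks

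*Combined protocol and SAP*

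**What the plan says.** Section 8.4 (Planned Interim Analysis): "Initial analysis of primary endpoints and safety endpoints will occur at 3 months post enrollment". The stated purpose is to find out whether the treatment protocols need important changes.

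Section 4.1 (General Design) says that endpoints are evaluated for the first time 6 months after enrollment, and that enrollment is rolling over months 0-6. Sections 4.1.1 and 8.2 define the primary endpoints as A1c at 6 and 12 months, each analysed as a mean and as the proportion at goal. Sections 4.1.2 and 8.2 list the 3- and 9-month values of the same two measures as secondary.

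Section 7.4.4 (Final Study Visit) says that "an interim analysis of efficacy will occur at the 6 month point". Section 2.1 treats 6 months as the assured assessment of the primary endpoints and 12 months as something done if possible.

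Section 5.7.1 lists "Demonstration of efficacy that would warrant stopping" among the reasons to suspend or end the study, and also lists futility. No boundary or threshold goes with either.

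On tests, section 8.2 says that differences in continuous variables "will be analyzed using paired, 2-tailed t tests" and that categorical ones use the "McNemar test for binary matched-pairs data". The only alpha in the document is the 0.050 in the power calculation of section 8.1.

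**The concern.** The first analysis of the endpoints cannot be at both 3 and 6 months, and there is no primary endpoint at 3 months for section 8.4 to analyse. If the 6-month analysis is an interim, the primary analysis would be the 12-month one, which sections 4.1 and 7.4.4 make conditional on funding and logistics. A reader of the results could not tell which comparison was meant to carry the efficacy claim.

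Two consequences follow. First, with several times, two measures and no stated adjustment, the chance that at least one primary comparison is falsely positive exceeds 5%. Second, section 8.4 foresees changing the treatment protocols after an early look. The algorithm is the intervention and there is no control group, so a change would put more than one version of the program into a single before-after estimate. Nothing in the plan provides for recording the version or reporting by it.

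**Working it through.** **1. The plan's own figure.** Inputs from section 8.1: "SD for outcome = 2.4", "Within-subject A1c correlation coefficient (rwithin) of 0.928", "Sample size = 100", alpha 0.05, power 80%.

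- SD of change = 2.4 × √(2 × (1 − 0.928)) = 0.911; SE = 0.911/√100 = 0.0911.
- Detectable difference, normal approximation: (1.960 + 0.842) × 0.0911 = 0.255. With the noncentral t it is 0.2577.

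The stated 0.257 is reproduced. It is the figure for one two-sided test at 0.05, with no allowance for a second time or measure. For comparison, an equal split of alpha over two tests (0.025 each) gives 0.284.

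**2. Type I error.** Assume that every test is two-sided at 0.05, that there is no true change, and that the same patients contribute at each time.

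- Upper limit, independent tests: 1 − 0.95² = 0.0975 for two times; 1 − 0.95³ = 0.143 for three.
- All changes share one baseline, so they are correlated. If A1c has equal variance σ² and equal correlation r between visits, the covariance of two changes is σ²(1 − r) and each variance is 2σ²(1 − r), so their correlation is 0.5 whatever r is. The documents give no correlation between looks; 0.5 to 0.7 is used here.
- The correlation between the mean and the proportion-at-goal tests is also not given; 0.5 to 0.7 is assumed.

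Simulated chance of at least one |z| > 1.96:

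| Tests | Mean A1c only | Both measures |
|---|---|---|
| 6 months only | 5.0% | 8-9% |
| 6 and 12 months | 8.3-9.1% | 14-16% |
| 3, 6 and 12 months | 10.9-12.5% | 18-22% |

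A separate simulation of the actual paired t and McNemar tests (n = 100, correlation between visits 0.5, 0.7 or 0.928) gave 15-16% for both measures at two times and 21-22% at three, in line with the table.

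**3. Where the excess comes from.** For mean A1c at correlation 0.5, the excess over 5% is 9.1 − 5 = 4.1 points without a 3-month test and 12.5 − 5 = 7.5 points with one. More than half (4.1/7.5 = 55%) is there without section 8.4. With both measures (both correlations 0.5) it is 16.1 − 5 = 11.1 of 21.9 − 5 = 16.9 points, about two thirds.

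**4. Version mixing.** Section 4.1 equates 6 months post enrollment with months 6-12 of the study. By the same conversion, 3 months post enrollment spans months 3-9. Take the two ends:

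- Change at month 3: a patient who entered at month 0 has 3 months on each version by the 6-month visit; anyone entering from month 3 has only the new one.
- Change at month 9: patients entering up to month 3 have finished 6 months on the old version; one entering at month 6 has 3 months on each.

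Either way, the 6-month estimate mixes versions if a change is made. Section 10.6 separately schedules safety analyses at 3, 6, 9 and 12 months and contemplates altering the titration protocols, so the same mixing can arise there.

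**The case against.** The best defence is that section 8.4 describes an operational check: it names no test, no threshold and no efficacy claim. On that view the mention of primary endpoints at 3 months is loose wording for the same two measures, which are secondary endpoints at that time. Calling the 6-month analysis an interim is understandable when follow-up may run to 12 months. Much of this stands.

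A reader might infer that A1c is to be tested at 0.05 at 3, 6 and 12 months, with freedom to stop after each. The documents do not say that. The 0.05 appears only in the power calculation. The list in section 5.7.1 is general and tied to no analysis. The specific halting rule in section 10.5 concerns severe hypoglycemia, and continuing to 12 months depends on funding and logistics. Nor is the early look the main source of error inflation: two primary times and two measures already produce most of it.

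The practical effect may also be small. This is a single-group pilot. For the 1-point change that section 8.1 regards as clinically significant, z would be 1/0.24 = 4.2 (correlation between visits 0.5, assumed) to 1/0.0911 = 11 (0.928), so a higher null error rate would rarely alter the conclusion.

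What the defence does not remove is the conflict between sections 4.1, 7.4.4 and 8.4, or the absence of any rule for the stops listed in section 5.7.1. The study has an efficacy objective (section 3) and a powered efficacy test, so its primary analysis should be identifiable.

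**Conclusion.** The point holds as a conflict about timing and status, with a multiplicity problem that exists mostly without the 3-month look. The plan does not settle whether the 6-month analysis is primary or interim, and section 8.4 schedules an analysis of primary endpoints at a time when none is defined.

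If each primary test is run at two-sided 0.05, the 6- and 12-month tests give about 8-9% type I error for mean A1c and about 14-16% with both measures. A formal 3-month test would take these to about 11-12.5% and 18-22%. These figures rest on an inferred test level and on assumed correlations of 0.5-0.7 between looks and between measures. The larger pair applies only if the 3-month look is a formal test, which the plan does not state.

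Version mixing is a possibility, not a certainty. It needs a change to be made, and it could follow from the section 10.6 safety reviews as well as from section 8.4.

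**What to change.** - **Sections 4.1, 4.1.1, 7.4.4, 8.2 and 8.4:** name the 6-month analysis as the single primary analysis. Make 12 months, which is done only if possible, secondary alongside 3 and 9 months.
- **Section 8.4:** limit the 3-month review to safety and application errors, and state that it supports no efficacy conclusion or stop. Say whether its date is counted per patient or by calendar.
- **Section 5.7.1:** delete the efficacy and futility reasons, or tie each to a prespecified rule.
- **Data capture and section 8.2:** record the application and algorithm version at each visit, including after changes that follow section 10.6 reviews. If it changes, report the 6-month result by version.

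The cost is wording plus one logged field. Safety oversight is not reduced, because section 10.6 already provides for it. The 12-month result loses primary status, and 3-month A1c is reported only as a secondary endpoint. Two measures remain at 6 months, with about 8-9% error between them under the same assumptions. The plan should acknowledge this or rank the two measures.
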